9.2.3.1 Adverse Events

9.2.3.1.1 Time Period and Frequency for Collecting and Reporting Safety Event Information

9.2.3.1.1.1 Disease-related Events

Disease-related events are defined in Appendix 4.

Protocol Number: 20170199

Date: 16 August 2017 **Page 28 of 70**

The investigator is responsible for ensuring that all disease-related events observed by the investigator or reported by the subject that occur after signing of the informed consent through the EOS visit are reported using the Event eCRF.

Disease-related events assessed by the investigator to be more severe than expected and/or related to the investigational product and determined to be serious, must be reported on the Event eCRF as serious adverse events.

Disease-related events pre-defined for this study include: manifestations and complications of atherosclerotic vascular disease such as coronary artery disease, angina, myocardial infarction, ischemic stroke, transient ischemic attack, carotid artery disease, peripheral vascular disease (including complications such as claudication), and testing suggesting progression of atherosclerotic vascular disease.

9.2.3.1.1.2 Adverse Events

The adverse event grading scale to be used for this study will be the Common Terminology Criteria for Adverse Events (CTCAE) and is described in Appendix 4.

The investigator is responsible for ensuring that all adverse events observed by the investigator or reported by the subject that occur after signing of the informed consent through the EOS visit are reported using the Event eCRF.

9.2.3.1.1.3 Serious Adverse Events

The investigator is responsible for ensuring that all serious adverse events observed by the investigator or reported by the subject that occur after signing of the informed consent through EOS visit are reported using the Event eCRF.

All serious adverse events will be collected, recorded, and reported to the sponsor or designee within 24 hours, as indicated in Appendix 4. The investigator will submit any updated serious adverse event data to the sponsor within 24 hours of it being available.

The criteria for grade 4 in the CTCAE grading scale differs from the regulatory criteria for serious adverse events. It is left to the investigator's judgment to report these grade 4 abnormalities as serious adverse events.

9.2.3.1.1.4 Serious Adverse Events After the Protocol-required Reporting Period

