Date: 16 August 2017 **Page 49 of 70**

Appendix 4. Safety Events: Definitions and Procedures for Recording, Evaluating, Follow-up and Reporting

Definition of Disease-related Event

Disease-related Event Definition

- Disease-related events are events (serious or non-serious) anticipated to occur in the study population due to the underlying disease. See Section 9.2.3.1.1.1 for the list of disease-related events.
- Disease-related events that would qualify as an adverse event or serious adverse event:
 - An event based on the underlying disease that is worse than expected as
 assessed by the investigator for the subject's condition or if the investigator
 believes there is a causal relationship between the investigational
 product(s)/study treatment/protocol-required therapies and disease worsening,
 this must be reported as an adverse event or serious adverse event.
- Disease-related events that do not qualify as adverse events or serious adverse events:
 - An event which is part of the normal course of disease under study (eg, disease progression in oncology or hospitalization due to disease progression) is to be reported as a disease-related event.

Definition of Adverse Event

Adverse Event Definition

- An adverse event is any untoward medical occurrence in a clinical study subject irrespective of a causal relationship with the study treatment.
- Note: An adverse event can therefore be any unfavorable and unintended sign (including an abnormal laboratory finding), symptom, or disease (new or exacerbated) temporally associated with the use of a treatment, combination product, medical device, or procedure.

Events Meeting the Adverse Event Definition

- Any abnormal laboratory test results (hematology, clinical chemistry, or urinalysis)
 or other safety assessments (eg, electrocardiogram [ECG], radiological scans, vital
 signs measurements), including those that worsen from baseline, that are
 considered clinically significant in the medical and scientific judgment of the
 investigator (ie, not related to progression of underlying disease).
- Exacerbation of a chronic or intermittent pre-existing condition including either an increase in frequency and/or intensity of the condition.
- New conditions detected or diagnosed after study treatment administration even though it may have been present before the start of the study.
- Signs, symptoms, or the clinical sequelae of a suspected drug-drug interaction.

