 is the responsibility of the investigator to review all documentation (eg, hospital
 progress notes, laboratory, and diagnostics reports) related to the event.
- The investigator will then record all relevant adverse event/disease-related event/serious adverse event information in the Event electronic case report form (eCRF).
 - Additionally, the investigator is required to report a fatal disease-related event on the Event eCRF.
- The investigator must assign the following adverse event attributes:
 - Adverse event diagnosis or syndrome(s), if known (if not known, signs or symptoms);
 - Dates of onset and resolution (if resolved);
 - Severity (or toxicity defined below);
 - Assessment of relatedness to investigational product, other protocol-required therapies, or devices; and
 - Action taken.
- If the severity of an adverse event changes from the date of onset to the date of resolution, record as a single event with the worst severity on the Event eCRF.
- It is not acceptable for the investigator to send photocopies of the subject's medical records to Amgen in lieu of completion of the Event eCRF page.
- If specifically requested, the investigator may need to provide additional follow-up
 information, such as discharge summaries, medical records, or extracts from the
 medical records. In this case, all subject identifiers, with the exception of the
 subject number, will be blinded on the copies of the medical records before
 submission to Amgen.
- The investigator will attempt to establish a diagnosis of the event based on signs, symptoms, and/or other clinical information. In such cases, the diagnosis (not the individual signs/symptoms) will be documented as the adverse event/serious adverse event.

Date: 16 August 2017 Page 53 of 70

Evaluating Adverse Events and Serious Adverse Events

Assessment of Severity

The investigator will make an assessment of severity for each adverse event and serious adverse event reported during the study. The assessment of severity will be based on:

The Common Terminology Criteria for Adverse Events (CTCAE), version 4.0 which is available at the following location:

http://ctep.cancer.gov/protocolDevelopment/electronic_applications/ctc.htm.

Assessment of Causality

- The investigator is obligated to assess the relationship between investigational product and device and each occurrence of each adverse event/serious adverse event.

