5.3 Other Related Definitions

Analytical Study Week Assignments

Analytical windows will be used to assign parameters to study weeks. The algorithm is provided in Appendix A. .

Investigational Product (IP)

IP is Repatha 420 mg QM SC.

IP Exposure Period in Months

IP Exposure Period = [min (Last IP Dose Date + 28 days, EOS Date) – First IP Dose Date + 1] / 365.25 * 12

Treatment Emergent Adverse Events

Events are categorized as Adverse Events (AEs) starting on or after first dose of investigational product as determined by the flag indicating if the value of the Events eCRF question "Did event start before first dose of investigational product?" is No or

Protocol Number: 20170199

Date: 09 March 2019 Page 10 of 19

missing and up to including 30 days after the end of investigational product or the End of Study date, whichever is earlier.

Treatment Emergent Disease-Related Events

Treatment emergent disease-related events are events categorized as Disease-related Events (DREs) starting on or after first dose of investigational product as determined by the flag indicating if the value of the Events eCRF question "Did event start before first dose of investigational product?" is No or missing and up to including 30 days after the end of investigational product or the End of Study date, whichever is earlier.

Reflexive Approach for LDL-C and VLDL-C

For all analyses related to LDL-C and VLDL-C, unless specified otherwise, a reflexive approach will be used. When calculated LDL-C is less than 40 mg/dL or triglycerides are > 400 mg/dL, the ultracentrifugation LDL-C and VLDL-C value from the same blood sample will be used instead of calculated LDL-C and VLDL-C, if available.

6. Analysis Sets

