9.6 Safety Analyses

9.6.1 Analyses of Primary Safety Endpoint(s)

Subject incidence of treatment-emergent adverse events will be summarized.

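### Adverse events that start in screening and worsen after the first Repatha dose can be left out of the primary endpoint, and sites may not code them alike

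*SAP*

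**What the plan says.** The sole primary endpoint is safety: "Subject incidence of treatment-emergent adverse events will be summarized" (SAP 9.6.1). The protocol uses the term treatment-emergent without defining it, so SAP 5.3 governs: "Events are categorized as Adverse Events (AEs) starting on or after first dose of investigational product as determined by the flag". The start of the period is thus set by an answer on the case report form, to "Did event start before first dose of investigational product"; an event counts if the answer is No or missing. The period ends 30 days after the end of investigational product or at the End of Study date, whichever is earlier. SAP 5.3 uses the same start rule for disease-related events.

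Three protocol provisions bear on this:

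- **Collection (9.2.3.1.1.2).** Sites report "all adverse events observed by the investigator or reported by the subject that occur after signing of the informed consent through the EOS visit". The screening window is up to 4 weeks (9.1.1), and medical history runs only to the signing of consent (9.2.1.3).
- **Recording (Appendix 4, section on recording events).** The instruction for a grade that "changes from the date of onset to the date of resolution, record as a single event with the worst severity on the Event eCRF" leaves one entry per event. Onset and resolution dates are required attributes; the date of a change in severity is not.
- **Definition (Appendix 4, events meeting the adverse event definition).** The list includes "Exacerbation of a chronic or intermittent pre-existing condition including either an increase in frequency and/or intensity of the condition".

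**The concern.** A treatment-emergent definition is meant to capture what appears or gets worse on drug. This one captures only what starts on drug. An event that begins in the weeks between consent and day 1 and then worsens after Repatha belongs in the primary endpoint, but the start flag can exclude it.

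The omission runs one way: leaving out on-treatment worsening can only lower the reported incidence. The study exists to meet a post-marketing safety requirement, has about 30 subjects and plans no inference, so the reported count is the whole primary result. Little else in the plan would show the worsening. Table 2-1 schedules hematology, chemistry and urinalysis at screening only, so on-treatment safety rests mainly on event records, vital signs and the week 12 examination.

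**Working it through.** The plan gives no figure to reproduce: the sample size of about 30 has no stated rate or precision behind it. The check is a trace through the definitions, followed by an illustration of size.

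**Trace.** Take, as an example, grade 1 myalgia starting on day -5, ongoing at day 1, and reaching grade 3 after the first dose.

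1. It starts after consent, so it is an Event eCRF record and not medical history (Protocol 9.2.3.1.1.2 and 9.2.1.3).
2. Its severity changes before it resolves. Under the recording rule in Appendix 4 it stays one record, now at grade 3. Appendix 4 does not say in so many words that the onset date is kept, but this follows from one record running from onset to resolution.
3. The correct answer to the start question is Yes. SAP 5.3 counts only No or missing, so the event is not treatment-emergent.
4. No other text restores it. SAP 5.3 has no worsening provision, and SAP section 10 declares no changes from the protocol analyses.
5. The data as recorded cannot repair it. The record holds the worst grade without a date, so a programmer cannot tell whether the worsening came before or after the dose.

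**Where the trace stops.** An event that resolves in screening and recurs after dosing is a new event and counts. A missing flag counts. An exacerbation entered as a new record counts.

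**Size per subject.** With all 30 subjects dosed, one subject whose only on-treatment event is such a worsening moves the incidence by 1/30 = 3.3 percentage points.

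**Illustration. All three rates are assumptions; the documents give none.**

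- Share of subjects with a screening adverse event: 10% to 20%.
- Share of those whose event worsens on drug: 10% to 30%.
- Share of affected subjects who have another treatment-emergent event anyway, t: 30% to 70%, taken as independent.

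Subjects affected = 30 × (0.10 to 0.20) × (0.10 to 0.30):

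- low: 30 × 0.10 × 0.10 = 0.3
- high: 30 × 0.20 × 0.30 = 1.8

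Only those without another treatment-emergent event change the subject incidence, so multiply by (1 − t):

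- low: 0.3 × (1 − 0.70) = 0.09 subjects; 0.09/30 = 0.3 points
- high: 1.8 × (1 − 0.30) = 1.26 subjects; 1.26/30 = 4.2 points

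The chance that at least one of 30 subjects has such a worsening is 1 − (1 − w)^30, where w is the product of the first two rates. For w = 1% it is 1 − 0.99^30 = 26%; for w = 6% it is 1 − 0.94^30 = 84%.

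**The case against.** The strongest reply is that exclusion is not settled. Appendix 4 does not tie a pre-existing condition to the date of consent. Its adverse event definition covers disease that is new or exacerbated, and it excludes fluctuations of conditions present at the start of the study only when they do not worsen. A site could therefore enter the post-dose worsening of a chronic or intermittent screening condition as a new event. The eCRF instructions and completion guidelines, which might decide the matter, are not among the documents. This stands, and it limits the claim: loss is certain only where the single-record rule is followed. It does not remove the problem. The single-record rule addresses a change in severity directly, the exacerbation clause reaches only chronic or intermittent conditions, and nothing says which prevails. With about 15 sites, the primary endpoint could be coded in two ways.

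A reader might also infer that a screening event that turns serious or fatal, or leads to withdrawal after dosing, is lost from those tables too. The documents do not show this. Protocol 10.4.2.3.2 and SAP 9.6.2 list those tables alongside the treatment-emergent table and appear not to limit them to treatment-emergent events.

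On disease-related events, Appendix 4 already requires those worse than expected, or thought causally related, to be reported as adverse events. Only the remainder is exposed.

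Finally, the study is descriptive, with no comparator or decision threshold, and few events will qualify: they must start in a window of at most 4 weeks and still be ongoing at dosing, in subjects screened for known active infection and other significant disorders. That is fair as to size. It is not a reason to leave the definition of the only primary endpoint open.

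**Conclusion.** The point holds in a limited form. Under SAP 5.3 together with the single-record rule, an adverse event that starts between consent and day 1, is still ongoing, and worsens after Repatha is excluded from the primary endpoint. Under the exacerbation clause it could be counted, so coding may differ between sites.

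The number affected is probably small. The understatement of about 0.3 to 4.2 points rests wholly on the assumed rates and on independence. Two stronger conclusions are not supported. One is that every condition arising after consent is necessarily lost while every condition from before consent is counted. The other is that all 0.3 to 1.8 affected subjects translate into lost incidence (1 to 6 points); those with another treatment-emergent event are already counted.

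**What to change.** 1. **Protocol Appendix 4 and eCRF instructions.** State that when an adverse event with onset before the first dose increases in CTCAE grade or becomes serious on or after the first dose, the worsening is entered as a new Event record with the date of worsening as its onset. The first record keeps the worst grade reached before dosing. The new record then meets the existing SAP flag, and the worsening is counted once.
2. **SAP 5.3.** Add that such worsening, within the existing window, is treatment-emergent. Apply the same to disease-related events not already reported as adverse events.
3. **Data already collected.** Before database lock, query sites for the date of any worsening of events flagged as starting before the first dose. Without that date the SAP sentence cannot be applied to existing single records.

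Cost: Appendix 4 is protocol text, so this needs a minor amendment or clarification with IRB/IEC submission (Protocol Appendix 3), plus one SAP sentence and a few site queries. The reported incidence may rise slightly. No visit, treatment or sample size changes.

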The investigator must permit study-related monitoring, audits, IRB/IEC review, and regulatory agency inspections and provide direct access to source data documents.

Protocol Number: 20170199

Date: 16 August 2017 **Page 46 of 70**

The sponsor or designee is responsible for the data management of this study including quality checking of the data.

Clinical monitors will perform ongoing source data verification to confirm that data entered into the eCRF by authorized site personnel are accurate, complete, and verifiable from source documents; that the safety and rights of subjects are being protected; and that the study is being conducted in accordance with the currently approved protocol and any other study agreements, ICH GCP, and all applicable regulatory requirements per the sponsor's monitoring plan.

The investigator agrees to cooperate with the clinical monitor to ensure that any problems detected in the course of these monitoring visits, including delays in completing eCRFs, are resolved.

The Amgen representative(s) and regulatory authority inspectors are responsible for contacting and visiting the investigator for the purpose of inspecting the facilities and, upon request, inspecting the various records of the clinical study (eg, eCRFs and other pertinent data) provided that subject confidentiality is respected.

In accordance with ICH GCP and the sponsor's audit plans, this study may be selected for audit by representatives from Amgen's Global Research & Development Compliance and Audit function (or designees). Inspection of site facilities (eg, pharmacy, protocol-required therapy storage areas, laboratories) and review of study-related records will occur to evaluate the study conduct and compliance with the protocol, ICH GCP, and applicable regulatory requirements.

Retention of study documents will be governed by the Clinical Trial Agreement.

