8.3 Handling of Missing and Incomplete Data

8.3.1 Patterns of Missing Data

Subjects may be missing specific data points for various reasons. In general, data may be missing due to a subject's early withdrawal from study, a missed visit, or non-evaluability of a data point or an endpoint at a particular point in time. In the Data Issue Identification and Resolution (DIIR) processes, queries will be made to the sites to distinguish true missing values from other unknown values (eg, due to measurement or sample processing error).

All attempts will be made to capture missing or partial data for this trial prior to the database lock.

There will be no imputation for missing data.

Protocol Number: 20170199

Date: 09 March 2019 Page 12 of 19

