8.3.2 Handling of Incomplete Dates

Adverse event and concomitant medications with completely or partially missing dates will be queried. After the query is resolved, if the date is still incomplete with year only or year and month only, the start date will be imputed as described in Table below:

Table 8-1. Imputation Rules for Incomplete Dates

	Missing	Imputation	Exception
Start date (AE and concomitant medication)	Day	1	Default to Study Day 1 if an event starts the same year and month as Study Day 1
	Day/Month	1-Jan	Default to Study Day 1 if an event started the same year as Study Day 1

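### SAP 5.3 counts an event as treatment-emergent when the pre-dose question is blank, even if a complete onset date places it before first dose

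*SAP*

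**What the plan says.** - **Endpoint.** SAP 9.6.1: "Subject incidence of treatment-emergent adverse events will be summarized". This is the only primary endpoint.
- **Start of the window.** SAP 5.3 takes events "starting on or after first dose of investigational product as determined by the flag indicating if the value of the Events eCRF question" about onset before first dose. No and missing both qualify; Yes does not. The onset date has no part in this limit.
- **End of the window.** The same definition runs on to "missing and up to including 30 days after the end of investigational product or the End of Study date, whichever is earlier", so the upper limit is set by dates.
- **Disease-related events.** SAP 5.3 repeats the same rule for them.
- **Collection period.** Protocol 9.2.3.1.1 has the investigator ensure that events observed or "reported by the subject that occur after signing of the informed consent through the EOS visit are reported using the Event eCRF". Pre-dose events are therefore in the same data set.
- **Onset date.** Protocol Appendix 4 lists "Dates of onset and resolution (if resolved" among the attributes the investigator must assign.
- **Partial dates.** SAP Table 8-1 imputes incomplete start dates, with the exception "Default to Study Day 1 if an event starts the same year and month as Study Day 1".
- **Checks.** Under SAP 8.3.1, "queries will be made to the sites to distinguish true missing values from other unknown values". Protocol Appendix 3 adds: "Clinical monitors will perform ongoing source data verification to confirm that data" are accurate and verifiable. Neither names a comparison of the pre-dose answer with the onset date.

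**The concern.** A blank answer carries no information about timing, whereas a complete onset date does. SAP 5.3 lets the blank settle the matter. A subject whose only event occurred in screening, with a complete date and an unanswered question, would be reported as having had an event on treatment.

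At stake is the accuracy of the numerator of the one primary endpoint, and of the matching disease-related summary. The information needed to classify these events correctly is already collected, and every member of the full analysis set has a first-dose date to compare it with.

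**Working it through.** The plan states no figure on this point, so there is none to reproduce. The check applies the rule to each combination of entries and then sizes the one that the rule itself gets wrong.

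**1. The rule applied**

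| Pre-dose question | Complete onset date | Class under SAP 5.3 | Comment |
|---|---|---|---|
| Yes | before Study Day 1 | not emergent | consistent |
| No or blank | after Study Day 1 | emergent | consistent with the date |
| Blank | before Study Day 1 | emergent | contradicts the only information available |
| Yes | after Study Day 1 | not emergent | one of the two entries is wrong |
| No | before Study Day 1 | emergent | one of the two entries is wrong |
| Any | on Study Day 1 | by the answer | the date cannot order it; dosing comes last at the visit (Protocol 9.1.2) |

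The date-based end limit does not rescue the third row, because an onset before first dose is earlier than both upper limits.

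**2. Effect per subject.** With about 30 subjects (Protocol 10.1), 1/30 = 3.3 percentage points.

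**3. Subjects with an event only before dosing.** Inputs: 28 days of screening (the maximum, Protocol 5.3.2) and 85 days on study (Week 12 target day, SAP Appendix A). Assumptions not in the documents: a constant event hazard and a true treatment-emergent incidence p.

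h = −ln(1 − p)/85; P = (1 − exp(−28h)) × (1 − p)

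| p | P, in points | Subjects of 30 | Shift if 5% are blank (assumed) |
|---|---|---|---|
| 0.3 | 7.8 | 2.3 | 0.39 points, 0.12 subject |
| 0.5 | 10.2 | 3.1 | 0.51 points, 0.15 subject |
| 0.7 | 9.8 | 2.9 | 0.49 points, 0.15 subject |

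**4. Wider range, by event.** With 4 weeks before dosing, 12 weeks after, λ = −ln(1 − p)/12 and a share e of pre-dose events left blank:

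rise = 1 − (1 − p) × exp(−4λe) − p

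| p | e = 2% | e = 5% | e = 10% |
|---|---|---|---|
| 0.2 | 0.12 | 0.30 | 0.59 |
| 0.4 | 0.20 | 0.51 | 1.01 |
| 0.6 | 0.24 | 0.61 | 1.20 |
| 0.8 | 0.21 | 0.53 | 1.04 |

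These are percentage points and correspond to 0.04 to 0.36 of a subject. The extreme case, every pre-dose event blank (e = 100%), gives 5.7 to 10.5 points, or 1.7 to 3.2 subjects.

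**The case against.** **The error needs an unresolved blank.** Missing values are queried, monitors verify entries against source, and the database is cleaned before lock. With about 30 subjects, chasing blanks is practical. Treating missing as No may be only a defensive default, and a flag-against-date check may sit in data-management documents not available here. This stands, and it is why the expected effect is small. It does not remove the gap: for any blank left at analysis, the SAP gives a rule that ignores a usable date.

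**The question has a proper use.** Dosing comes last at the visit, so a calendar date cannot place a Study Day 1 event before or after it. This stands too, and the fix keeps the question for that case.

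A reader might also draw stronger conclusions that the documents do not support:

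- *That the whole definition rests on the flag.* Only the start limit does; the end limit uses dates.
- *That the rule drops post-dose events.* That happens only through a wrong Yes that survives query, source verification and cleaning. With an assumed 2% to 10% of post-dose events so mis-answered, incidence becomes 1 − (1 − p)^(1 − e), a loss of 0.4 to 3.8 points for p from 0.2 to 0.8. Those rates have no basis in the documents, and the cause would be an entry error, not the treatment of blanks.
- *That the date should always override the answer.* Dates can be mis-keyed or misremembered as well. An automatic override would drop a true post-dose event that carries an erroneous pre-dose date. The SAP does not address such conflicts expressly, and a query is the neutral remedy.
- *That Table 8-1 competes with SAP 5.3.* It fills in a date and classifies nothing. An event answered Yes stays out of the count whatever date is imputed.

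**Conclusion.** The point holds for one case: a blank answer with a complete onset date before Study Day 1. SAP 5.3 then counts a pre-dose event as treatment-emergent by rule, for adverse events and disease-related events alike.

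The expected effect is well under one subject across the 2% to 10% range. It rests on assumed blank rates, an assumed incidence, a constant hazard and the maximum screening period for everyone; shorter screening would make it smaller. The study is descriptive and no decision threshold depends on the result. This is a minor improvement in the accuracy of the headline figure.

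**What to change.** In SAP 5.3, for both adverse events and disease-related events:

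1. When the pre-dose question is blank and the onset date is complete, or complete enough to order against first dose, classify by onset date against first-dose date.
2. Keep blank as treatment-emergent only for onset on Study Day 1 or for a date too incomplete to order.
3. When an answered question and a complete date disagree, query the site before database lock, and let neither override the other silently.

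For consistent listings only, apply the Study Day 1 default of Table 8-1 to event start dates only when the answer is not Yes. This avoids listing an event recorded as pre-dose with a Study Day 1 onset. It does not change the count, because the answer already governs.

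The cost is a few sentences in the SAP, a small change to the derivation program and one edit check. No new data are needed.
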